#### 8.2.2.5 Cardiac toxicity:

- **Prior to initiation of treatment (i.e. after registration but prior to C1D1), for left ventricular ejection fraction (LVEF) below the institutional LLN or below 50%**, whichever is lower, treatment is not recommended. Consult with study chair prior to initiating treatment with vemurafenib and cobimetinib.
- For **grade 1 heart failure with EF  $\leq 40\%$** , delay cobimetinib until EF  $\geq 40\%$  and then resume at 1 dose level decreased
- For **grade 2 heart failure**, delay cobimetinib until grade  $\leq 1$  and EF  $\geq 40\%$ , and then resume at 1 dose level decreased.
- For **grade  $\geq 3$  heart failure**, discontinue cobimetinib.
- For **grade 2 ventricular arrhythmia**, delay vemurafenib until grade  $\leq 1$  then restart at 1 dose level decreased.
- For **grade  $\geq 3$  ventricular arrhythmia**, discontinue vemurafenib and cobimetinib.

#### 8.2.2.6 Investigations:

- **Prior to initiation of treatment (i.e., after registration but prior to C1D1), for QTc  $> 500$  msec**, treatment not recommended. Consult with study chair prior to initiating treatment with vemurafenib and cobimetinib.
- For **grade 3 QTc interval prolonged**, delay vemurafenib until grade  $\leq 2$  then restart at 1 dose level decreased. Electrolytes (K, Mg, and Ca) should be monitored and any electrolyte abnormalities should be corrected prior to reinstitution of therapy.
- For **third occurrence of grade 3 QTc interval prolonged**, discontinue vemurafenib and cobimetinib.
- For **grade 4 QTc interval prolonged**, discontinue vemurafenib and cobimetinib.

#### 8.2.2.7 Eye toxicity

- For **grade 2 uveitis**, delay vemurafenib until grade  $\leq 1$ , then resume at 1 dose level decreased.

- For **grade 3 or 4 uveitis**, discontinue vemurafenib and cobimetinib.
- For **grade 2 eye retinopathy**, delay cobimetinib until grade  $\leq 1$ , then resume at 1 dose level decreased.
- For **grade 3 or 4 retinopathy**, discontinue cobimetinib.
- For **retinal vascular disorder- retinal vein occlusion grade  $\geq 2$** , discontinue cobimetinib.

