#### 8.2.2.15 Other toxicities

- For **all other grade 3 toxicities considered at least possibly related to treatment**, omit the responsible drug(s) until toxicity improves to  $\leq$  grade 1, then resume the responsible drug(s) at the next lower dose level.
- For **all other grade 4 toxicities considered at least possibly related to treatment**, discontinue the responsible drug(s). If the responsible drug is vemurafenib, discontinue both cobimetinib and vemurafenib. The exception is hyperglycemia (see [Section 8.2.4](#)) or electrolyte abnormalities that can be managed with medical therapy, where the responsible drugs do not need to be discontinued if the adverse event is adequately managed.

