### 9.3.2 AEs of special interest related to vemurafenib + cobimetinib

In addition to routine reporting requirements as outlined in [Sections 9.1](#) and [9.2](#), the following adverse events of special interest must be reported via routine event reporting regardless of attribution, and may necessitate reporting via CTEP-AERS (see [Section 9.4](#)). If a grade is not specified in the table below, then reporting is required for any grade of that AE. These events must be reported in Rave in same time frame as serious adverse events (see table in [Section 9.4](#)).

Adverse Events: Other CRF should be used to report AEs occurring between registration and within 30 days of the patient's last treatment date.

Adverse Events: Late CRF should be used to report AEs occurring greater than 30 days after the patient's last treatment date.

CTCAE v4.0 Term	CTCAE v4.0 System Organ Class (SOC)
Grade $\geq$ 2 Heart failure	Cardiac disorders
Grade $\geq$ 2 Left ventricular systolic dysfunction	Cardiac disorders
Optic nerve disorder	Eye disorders
Retinal detachment (including neurosensory retinal detachment)	Eye disorders
Retinal vascular disorder (including retinal vein occlusion)	Eye disorders
Retinopathy (including serous retinopathy and central serous chorioretinopathy)	Eye disorders
Eye disorders (other) – (including retinal pigment epithelium detachment, or any other eye disorders)	Eye disorders
Events suggestive of Drug Induced Liver Injury (report as Hepatobiliary disorders – Other, specify)	Hepatobiliary disorders
Grade $\geq$ 2 Ejection fraction decreased	Investigations
Grade $\geq$ 3 Electrocardiogram QT corrected interval prolonged	
Grade $\geq$ 3 Hemorrhage event (report per specific CTCAE hemorrhage location)	Eye disorders Gastrointestinal disorders Hepatobiliary disorders Injury, poisoning and procedural complications Renal and urinary disorders Reproductive system and breast disorders Respiratory, thoracic and mediastinal disorders
Intracranial hemorrhage	Nervous system disorders

Treatment related secondary malignancy	Neoplasms benign, malignant and unspecified (incl cysts and polyps)
Neoplasms benign, malignant and unspecified (incl cysts and polyps) – Other, including: 
 
• New or worsening malignancies
 
• Non-cutaneous squamous cell carcinoma
 
• Skin cancers
 
• Gastrointestinal polyps
 
	Neoplasms benign, malignant and unspecified (incl cysts and polyps)

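### Section 8.2.2.7 gives no cobimetinib rule for retinal detachment, so the general rule leaves grade 2 without a dose action and allows conditional re-challenge after grade 3; a lesser fault is that the EF hold in 8.2.2.5 depends on the recorded term

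*Combined protocol and SAP*

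**What the plan says.** Footnote A of the study calendar (Section 5.0) orders periodic on-treatment eye exams, including a retinal exam, and refers to 8.2.2.7 for dose changes. That section covers uveitis, retinopathy and retinal vein occlusion. For "grade 2 eye retinopathy" cobimetinib is held to grade 1 or less and resumed one level lower. For "grade 3 or 4 retinopathy" it is discontinued. Retinal vein occlusion of grade 2 or higher also stops it. Retinal detachment is not named anywhere in Section 8.

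Section 8.2 says the dose rules use CTCAE version 4.0 descriptors. The list of events of special interest in 9.3.2 has one row beginning "Retinal detachment (including neurosensory retinal detachment" and a different row beginning "Retinopathy (including serous retinopathy and central serous chorioretinopathy". The cobimetinib risk list (9.5.2) and the nursing guidelines in 10.2 both name retinal detachment.

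Events without a rule of their own go to 8.2.2.15, which covers "all other grade 3 toxicities considered at least possibly related to treatment" and, in a second bullet, related grade 4 events. It has no bullet for grade 2. At grade 4 it adds: "If the responsible drug is vemurafenib, discontinue both cobimetinib and vemurafenib".

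For the heart, calendar footnote C orders Echo or MUGA and refers to 8.2.2.5. The on-treatment EF trigger there is worded for "grade 1 heart failure with EF" at or below 40%, with resumption at 40% or above. Section 9.3.2 lists heart failure, "Left ventricular systolic dysfunction" and decreased ejection fraction as separate terms.

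**The concern.** A site that follows the stated rules takes a less protective action for retinal detachment than for retinopathy at grades 2 and 3, although the trial orders the exam that would find it. It looks like an omission. Eligibility (3.3.6) excludes retinal pathology that is a risk factor for neurosensory detachment. Section 9.5.2 places detachment in a more frequent column (up to 20%) than retinal vein occlusion (under 3%), yet only the latter has a named rule. Where the calendar means the general rule it says so: footnote 8 sends hypoxia to 8.2.2.15.

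The general rule also requires attribution to treatment, which the retinopathy bullets do not. Section 8.1.16 notes that these patients have tumour-related visual field defects, so attribution of a visual event may be uncertain. At stake is continued or resumed cobimetinib exposure after an event that may affect sight.

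**Working it through.** **Retinal detachment against retinopathy (cobimetinib).** The plan states no figure to reproduce here, so the rules are traced by grade.

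| Grade | Retinopathy (8.2.2.7) | Retinal detachment (8.2.2.15, if at least possibly related) |
|---|---|---|
| 2 | hold to grade ≤1, resume one level lower | no dose action |
| 3 | discontinue | omit to grade ≤1, resume one level lower; discontinued if held >28 days (8.2) |
| 4 | discontinue | discontinue the responsible drug(s); both if vemurafenib is responsible |

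The rules differ at grades 2 and 3. At grade 4 they agree on cobimetinib if it is judged responsible, or if vemurafenib is.

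**Size at grade 2.** The documents give no grade 2 rate. The column in 9.5.2 gives only a ceiling for all grades: 0.20 × 36 = 7.2 patients. That is a column limit, not an estimate.

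**Size at grade 3.** Section 1.6.3 reports retinal detachment in 2.4% against 0%, under a heading printed as grade >3, with 254 patients on the combination.
- If the heading means ≥3: 0.024 × 254 = 6.1, so about 6 of 254. The exact (Clopper-Pearson) 95% interval is 0.0087 to 0.0507.
- Applied to the maximum accrual of 36: 36 × 0.024 = 0.86; interval 36 × 0.0087 = 0.31 to 36 × 0.0507 = 1.83.
- Scaled to four cycles: 4 × 28 / 30.44 = 3.68 months, and 3.68 / 12.3 = 0.299, where 12.3 months is that trial's median PFS (Section 1.5). This gives 0.86 × 0.299 = 0.26 patients (0.09 to 0.55). It assumes a constant rate, with PFS standing in for exposure. Cohort B may be treated longer.
- If the heading is taken literally as >3, these events bear on no grade at which the rules differ, and the difference is zero.

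**EF rule.** The hold set is EF ≤40% and the resume set is EF ≥40%. They intersect at EF = 40%, where both instructions apply. A patient improving from grade 2 to grade 1 heart failure at EF 40% may resume under the grade 2 bullet and must be held under the grade 1 bullet. The same EF recorded only as decreased ejection fraction or left ventricular systolic dysfunction has no bullet in 8.2.2.5 or 8.2.2.6 and goes to 8.2.2.15. No graded rate is given for these two terms.

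**The case against.** Several safeguards exist, and they limit the point:

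- A reader might infer that the protocol asks nothing at grade 2. It does not support that. Section 9.3.2 requires detachment of any grade, whatever the attribution, to be reported in the time frame for serious events. The gap is in dosing only.
- A reader might infer free re-challenge at grade 3. In fact recovery to grade 1 or less, a lower dose and a hold of no more than 28 days are all required.
- Section 8.2 applies the greatest modification when several events are recorded. If retinopathy accompanies detachment, or heart failure accompanies an EF term, the stricter action already governs. The gap remains when only the unruled term is recorded.
- Sections 5.0, 8.2, 12.1 and 12.3 allow clinical judgment, point to the investigator's brochure or study chair, and permit stopping. They name no hold at grade 2 and do not bar re-challenge at grade 3. What the brochure says cannot be seen from these documents.
- The documents give no CTCAE grade definitions. Equal grades under the two terms may not mean equal severity. This stands as a limit on the comparison.
- A reader might infer that a low EF under the other terms escapes action. That cannot be shown: 8.2.2.15 acts at grades 3 and 4, and the EF cut-offs for those grades are not given. What can be shown is that the EF ≤40% trigger depends on the recorded term.
- The overlap at exactly 40% is a single value and a drafting matter.

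**Conclusion.** The omission is real and should be corrected. For retinal detachment recorded alone, the dose rules require nothing at grade 2 and permit conditional re-challenge at grade 3, while the neighbouring retinopathy rule holds and then stops cobimetinib. The grade 2 gap cannot be sized, and 7.2 of 36 should not be read as an expected count. At grade 3 the point estimate is about 0.9 of 36 patients (0.3 to 1.8) without scaling, assuming that the melanoma rate carries over and that the printed heading means grade 3 or higher; it is zero on the literal reading. The EF points are secondary and minor.

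A reader might look for an effect on the response rate or the two-stage design. None is claimed: no sample size, power or error rate depends on these rules.

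**What to change.** 1. In 8.2.2.7, extend the retinopathy bullets to retinal detachment, including neurosensory. At grade 2, hold cobimetinib to grade ≤1 and resume one level lower; at grade 3 or 4, discontinue cobimetinib. State that 8.2.2.15 still governs vemurafenib when it is judged responsible: omit then reduce at grade 3, stop both drugs at grade 4. Without that sentence, a named rule would take detachment out of the general rule and lose the present grade 3 hold of vemurafenib.
2. In 8.2.2.5, apply the cobimetinib hold to any on-treatment EF ≤40%, whichever term is recorded. Change the resume limit to EF >40% in both the grade 1 and the grade 2 heart failure bullets. Keep the stop at heart failure grade 3 or higher, and keep 8.2.2.15 in force where it is stricter.

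A grade 2 EF fall that stays above 40% would still have no required action; the documents offer no other on-treatment threshold to use.

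The cost is a short wording change and no new test. The downside is a few more cobimetinib holds or stops; Sections 7.1 and 8.2 allow vemurafenib to continue alone.

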#### 8.2.2.8 Hematologic toxicity

For **grade 4 anemia**, delay cobimetinib until grade  $\leq 3$ , then resume at 1 dose level decreased.

#### 8.2.2.9 Hypersensitivity:

- For **grade 2 or 3 allergic reaction**, delay cobimetinib and vemurafenib until grade  $\leq 1$ .
- For **grade  $\geq 4$  allergic reaction**, discontinue cobimetinib and vemurafenib.

#### 8.2.2.10 Pulmonary toxicity

- For **grade 2 pneumonitis**, delay cobimetinib until grade  $\leq 1$ , then resume at 1 dose level decreased.
- For **grade 3 or 4 pneumonitis**, discontinue cobimetinib.

#### 8.2.2.11 Vascular toxicity:

- For **grade 2 or 3 hypertension**, delay cobimetinib until grade  $\leq 1$ , then resume at 1 dose level decreased.
- For **grade 4 hypertension**, discontinue cobimetinib.

#### 8.2.2.12 Hemorrhage:

- For **grade 3 hemorrhage**, delay cobimetinib until grade  $\leq 1$  (or grade  $\leq 2$  if no grade 1 exists), then resume at 1 dose level decreased.
- For **grade 4 hemorrhage**, discontinue cobimetinib.

#### 8.2.2.13 New primary malignancies (cutaneous and non cutaneous)

No dose modification for cobimetinib required.

#### 8.2.2.14 Rhabdomyolysis and CPK elevations

For **grade 4 CPK** elevation or CPK elevation and myalgia, withhold cobimetinib for up to 4 weeks. If improved to Grade 3 or lower, resume at the next lower dose level

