**Table 3 Most Common Adverse Events (Occurring in >20% of Patients) in Study GO28141**

	Vemurafenib n=	Vemurafenib + cobimetinib n=
Diarrhea	67 (28%)	144 (56.7%)
Rash	85 (35.6%)	99 (39%)
Arthralgia	96 (40.2%)	83 (32.7%)
Fatigue	74 (31%)	82 (32.3%)
Nausea	57 (23.8%)	99 (39%)
Pyrexia	53 (22.2%)	66 (26%)
Photosensitivity	38 (15.9%)	72 (28.3%)
Alopecia	70 (29.3%)	35 (13.8%)
ALT increase	43 (18%)	60 (23.6%)
Hyperkeratosis	68 (28.5%)	26 (10.2%)
AST increase	30 (12.6%)	56 (22%)
CPK increase	7 (2.9%)	76 (29.9%)
Vomiting	29 (12.1%)	54 (21.3%)

ALT = alanine aminotransferase; AST = aspartate aminotransferase; CPK = creatine phosphokinase.

At least one Grade > 3 AE was reported in 65% of patients treated with cobimetinib + vemurafenib and 59% of patients treated with placebo + vemurafenib. Table 3 tabulates the Grade >3 AEs occurring in at least 2% of patients in either arm. The most common Grade >3 AEs in patients treated with cobimetinib + vemurafenib than in patients treated with placebo + vemurafenib were ALT increased (11.4% vs. 6.3% of patients), blood creatine phosphokinase increased (10.2% vs. 0%), AST increased (8.3% vs. 2.1%), diarrhea (6.3% vs. 0%), blood alkaline phosphatase increased (4.3% vs. 1.7%), hyponatremia (2.4% vs. 0.4%), photosensitivity reaction (2.4% vs. 0%), and retinal detachment (2.4% vs. 0%). Serious adverse events (SAEs) occurred in 75 patients (29.5%) treated with cobimetinib + vemurafenib, of which, 46 SAEs were considered related to study treatment. SAEs occurred in 60 patients (25.1%) treated with placebo + vemurafenib, of which, 35 SAEs were considered related to study treatment.

The three most common SAEs in patients treated with cobimetinib + vemurafenib were pyrexia (2.4% of patients), dehydration (2.0%), and rash (1.6%). The three most common

SAEs in patients treated with placebo+vemurafenib were pyrexia, keratoacanthoma, and pleural effusion (1.3% each).

As of the clinical cutoff date, 36 of 254 patients (14.2%) who received cobimetinib+vemurafenib and 48 of 239 patients (20.1%) who received placebo+vemurafenib had died. In most cases, the primary cause of death was attributed to disease progression.

Six patients in the cobimetinib+vemurafenib arm and 3 patients in the placebo+vemurafenib arm were reported to have Grade 5 AEs. There were no patterns with respect to the type of Grade 5 events reported, and for most events the patient's underlying disease was considered to contribute to the cause of the event.

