### 8.2.4 Hyperglycemia and metabolic effects

Patients should be instructed to report symptoms associated with hyperglycemia such as thirst, frequent urination, and blurred vision. Use of oral anti-hyperglycemic agents, such as metformin, for patients experiencing Grade  $\geq 2$  hyperglycemia may be implemented. For Grade 3 or greater hyperglycemia, consider increasing dose of anti-hyperglycemic agents, such as metformin, and initiating insulin. Anti-hyperglycemic agents should be used to control severe hyperglycemia per institutional standard of care. Recommended management of hyperglycemia:

- For Grade 2 or greater hyperglycemia, consider initiating oral glucose lowering medication such as metformin
- For Grade 3 or greater hyperglycemia, hydration status should be clinically assessed. If clinical assessment is consistent with dehydration, fluids should be given as clinically appropriate. If patient is asymptomatic, consider increasing oral glucose lowering medication. If patient is symptomatic, rapid/short acting insulin should be initiated according to institution sliding scale coverage as per institutional guidelines, and consider increasing oral glucose lowering medication. For persistent Grade 3 or greater hyperglycemia, please consult with endocrinologist. Grade 4 hyperglycemia should lead to agent discontinuation only if it does not respond to initial medical treatment with appropriate glucose lowering medication.

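### The dose-modification rules for CPK elevation, anemia, hyperglycemia and electrolyte abnormalities do not fit together, so sites following the text can reach different hold and restart decisions

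*Combined protocol and SAP*

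**What the plan says.** Four sections of the combined protocol and SAP bear on the point.

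- **Section 8.2.2.14 (CPK).** The trigger is grade 4 CPK "elevation or CPK elevation and myalgia, withhold cobimetinib for up to 4 weeks". The restart rule is "If improved to Grade 3 or lower, resume at the next lower dose level".
- **Section 8.2.2.8 (anemia).** The only rule is "For grade 4 anemia, delay cobimetinib until grade" 3 or lower, then resume one dose level down. Grade 3 anemia is not mentioned.
- **Section 8.2.2.15 (other toxicities).** For all other related grade 3 toxicities the instruction is "omit the responsible drug(s) until toxicity improves to" grade 1 or lower, then resume one level down. For all other related grade 4 toxicities the responsible drug is discontinued. Hyperglycemia and medically manageable electrolyte abnormalities are excepted, "where the responsible drugs do not need to be discontinued if the adverse event is adequately managed". The exception is written in the grade 4 bullet only.
- **Section 8.2.4 (hyperglycemia).** Grade 3 is managed with fluids, oral agents and insulin, and no study-drug hold or reduction is stated. "Grade 4 hyperglycemia should lead to agent discontinuation only if it does not respond to initial medical treatment".

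The general rules in Section 8.2 add that an agent held for more than 28 days is discontinued.

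**The concern.** A dose-modification table should give one action for each event and grade. Here three places do not. A medically controlled grade 3 electrolyte or glucose event carries an explicit hold and reduction, while the same event at grade 4, if adequately managed, carries neither. A hold for CPK elevation with myalgia can start at a grade that the restart test does not distinguish from recovery. CPK elevation without myalgia and anemia that begin at grade 3 either fall under a stricter restart rule than grade 4 or have no rule at all.

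What is at stake is patient safety and uniform exposure. The primary endpoint is response in the first four 28-day cycles, in cohorts of 16. A 28-day hold is 28/112 = 25% of that window. If sites resolve the text differently, both exposure and the toxicity summary depend partly on which bullet a site applied.

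**Working it through.** No figure in the plan needs reproducing. The check is a comparison of the rules by event and grade.

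| Event (related to treatment) | Section | Action as written |
|---|---|---|
| CPK, grade 4 | 8.2.2.14 | Hold cobimetinib up to 4 weeks; restart at grade 3 or lower, one level down |
| CPK elevation with myalgia, grade 1 to 3 | 8.2.2.14 | Same hold and same restart test |
| CPK without myalgia, grade 3 from onset | none of its own | 8.2.2.15 if covered (hold to grade 1 or lower), otherwise no rule |
| Anemia, grade 4 | 8.2.2.8 | Hold cobimetinib; restart at grade 3 or lower, one level down |
| Anemia, grade 3 from onset | none of its own | 8.2.2.15 if covered (hold to grade 1 or lower), otherwise no rule |
| Electrolytes or hyperglycemia, grade 3 | 8.2.2.15 | Hold to grade 1 or lower, one level down |
| Hyperglycemia, grade 3 | 8.2.4 | Medical management; no hold or reduction stated |
| Electrolytes or hyperglycemia, grade 4, adequately managed | 8.2.2.15 (and 8.2.4 for hyperglycemia) | Discontinuation not required; no hold or reduction stated |
| The same, not adequately managed | 8.2.2.15 (and 8.2.4 for hyperglycemia) | Discontinue |

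**Step 1, hyperglycemia and electrolytes.** Sections 8.2.2.1 to 8.2.2.14 contain no rule for either. (Section 8.2.2.6 asks for electrolytes to be corrected before restarting after QTc prolongation, which is not a rule for electrolyte toxicity.) Section 8.2.2.15 also treats them as residual toxicities, since an exception in the grade 4 bullet is needed only if the bullet would otherwise reach them. The grade 3 bullet therefore reaches them too, and it has no exception. For hyperglycemia this conflicts with Section 8.2.4. For electrolytes no other section exists to resolve it.

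**Step 2, CPK with myalgia.** The restart test is grade 3 or lower. A patient held at grade 1, 2 or 3 is already in that range, so the test names no grade to be reached.

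**Step 3, onset at grade 3.** If all other grade 3 toxicities means any event and grade without its own rule, grade 3 CPK and grade 3 anemia wait for grade 1 or lower, while grade 4 restarts at grade 3 or lower. With the 28-day limit in Section 8.2, a patient who was never above grade 3 and stays at grade 2 would lose the drug, while a patient who goes from grade 4 to grade 3 in time would resume it. If the phrase means event types not listed above, these patients have no rule. The text does not say which.

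**Step 4, size.** Expected count = 32 evaluable patients (Section 13.2.2) × rate, assuming that the rates carry over.

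- CPK with the combination (Section 1.6.3, study GO28141): "blood creatine phosphokinase increased (10.2% vs. 0" percent in the control arm. 32 × 0.102 = 3.3. The section prints the grade as above 3; it is taken here as grade 3 or higher.
- Hyponatremia: 2.4% with the combination (same section) to 9.6% with cobimetinib alone (Section 1.6.2). 32 × 0.024 = 0.8; 32 × 0.096 = 3.1.
- Anemia, cobimetinib alone (Section 1.6.2): 32 × 0.078 = 2.5.
- Hypokalemia, cobimetinib alone (Section 1.6.2): 32 × 0.061 = 2.0.

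The CPK count is an upper bound for the patients in dispute, because it includes grade 4 events that Section 8.2.2.14 covers. None of the counts is limited to related events, which Section 8.2.2.15 requires.

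**The case against.** The strongest reply is that a specific rule displaces a general one. Section 8.2.2.15 covers other toxicities, and CPK and anemia have their own sections. This stands for a patient who falls from grade 4 to grade 3. A reader might infer that such a patient is told both to resume and to stay off drug, but the documents do not support that: Sections 8.2.2.14 and 8.2.2.8 govern and say resume. It does not settle onset at grade 3, which those sections do not name.

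A reader might also infer that a restart at grade 3 is itself a mistake. It is not. Thresholds vary by event elsewhere: nausea, vomiting and QTc prolongation restart at grade 2 or lower.

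On CPK with myalgia, it can be said that the patient must have improved, so the test is not met on the day of the hold, or that grade 4 governs both triggers. The first point is fair, but improvement with no stated target is still not a usable end point. The second would make the myalgia trigger redundant, since grade 4 CPK already triggers the hold alone.

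On hyperglycemia and electrolytes, the exception waives discontinuation only, and the grade 3 bullet never requires discontinuation. That is correct. It leaves the explicit grade 3 hold facing silence at grade 4, and the mismatch with Section 8.2.4.

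Finally, Section 8.2 points sites to the investigator brochures and the study chair for further guidance, and the CPK and anemia rules hold cobimetinib only. Both points reduce the consequence but do not remove the ambiguity.

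**Conclusion.** The concern holds in three parts. Related grade 3 hyperglycemia and electrolyte events carry a hold and reduction that is not stated for adequately managed grade 4 events and that Section 8.2.4 does not mention. CPK elevation with myalgia has no working restart target when it begins at grade 1 to 3. CPK elevation without myalgia and anemia beginning at grade 3 have either an inverted rule or none, depending on a phrase the protocol does not define.

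A reader might conclude that grade 3 is in general treated more strictly than grade 4. For hyperglycemia and electrolytes that is true only of adequately managed grade 4 events; others are discontinued. For CPK and anemia it is true only if the residual rule covers unlisted grades.

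The number of patients who could meet one of these rules is small but not negligible: up to about 3.3 of 32 for CPK, 0.8 to 3.1 for hyponatremia, 2.5 for anemia and 2.0 for hypokalemia. This rests on melanoma and solid-tumor rates applying to this population. The counts should not be added, since one patient may have several events. No effect on sample size, power or type I error follows. The point should be fixed because sites acting in good faith can reach opposite hold or restart decisions.

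**What to change.** The study chair and drug sponsor should reconcile Sections 8.2.2.8, 8.2.2.14, 8.2.2.15 and 8.2.4 so that each event and grade has one action. The text should:

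- state whether all other grade 3 toxicities includes grade 3 CPK elevation and grade 3 anemia;
- state whether the exception for medically managed hyperglycemia and electrolyte abnormalities also applies at grade 3, and what happens to dosing at grade 4 when the exception is used;
- give CPK elevation with myalgia a restart condition that works for every grade that triggers the hold.

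No threshold is proposed here; that choice is clinical. The cost is wording in four short sections and a notice to sites. No tests are added, since CPK, glucose, electrolytes and blood counts are already on the Section 5.0 calendar.
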